9.6.5 Supplementary analyses

Supplementary analyses are conducted for other quantities of interest.

9.6.5.1 *ARR up to EOT + 7 days for confirmed relapses*

The primary efficacy model will be repeated only including confirmed relapses up to EOT + 7 days as a response variable, treatment as a factor, the stratification variables and the number of relapses in the year prior to study entry (≤ 1 [or missing] and ≥ 2) as covariates based on the FAS. The model is offset by the log of number of days from randomization up to EOT + 7 days.

The following sensitivity analyses related to confirmed relapses up to EOT + 7 days are conducted:

- *ARR based on confirmed relapses up to EOT + 7 days on the FAS – unadjusted analysis:*

Same analysis as for the main analysis, but with number of confirmed relapses up to EOT + 7 days as a response variable, and treatment as the only factor in the model, i.e., not adjusting for covariates, including stratification variables. The analysis is conducted to assess the effect of adjusting for covariates.

- *ARR based on confirmed relapses up to EOT + 7 days on the FAS – multiple imputation between EOT + 7 days and theoretical Week 108:*

Furthermore, sensitivity analyses based on multiple imputation are conducted based on different assumptions following treatment discontinuation to assess the hypothetical effect if subjects would have stayed on treatment up to Week 108. Multiple imputation methods for count data are applied as for the sensitivity analyses related to the primary analysis [Section 9.6.4.3 and Section 10.1.1]. For subjects who have prematurely discontinued treatment post-treatment events, i.e., the number of relapses between EOT + 7 and theoretical Week 108, will be imputed.

Imputation of events is conducted with the following MI approaches: Missing at Random (MAR), Copy reference, Jump to reference. The corresponding interpretations are detailed in Section 9.6.4.3, only that imputation is now conducted post EOT + 7 days instead of post-study withdrawal.

The resulting rate ratio and corresponding 99% and 95% CIs will be reported and presented in tables and graphically.

9.6.5.2 ARR based on confirmed relapses up to EOS - Per protocol analysis

Same analysis as for the main analysis, but with number of confirmed relapses up to EOS (per-protocol) as a response variable and the logarithm of time (in years) between randomization and EOS (or up to per protocol exclusion date) as an offset variable based on the PPS. Conducted to check the consistency of the treatment effect in the per protocol analysis with the effect in the main analysis. This analysis will evaluate whether a bias in evaluating the treatment effect has been introduced in the FAS due to major protocol deviations.

9.6.5.3 ARR based on all relapses up to EOS on the FAS

Same analysis as for the main analysis, but with number of all relapses up to EOS as a response variable. All other aspects of the model are as per the main analysis. This analysis is described to check the consistency of the treatment effect on all relapses and that no bias was introduced in the confirmation of relapses.

The following sensitivity analysis is conducted

- *ARR based on all relapses up to EOS including derived stratification variable:* Same analysis as for the main analysis, but instead of adjusting for the stratification variables from IRT adjust for eCRF-derived stratification variables.

9.6.5.4 ARR based on confirmed relapses up to start of new DMT for MS on the FAS

Same analysis as for the main analysis, but with number of confirmed relapses up to the minimum of EOS date, or the start of a new DMT for MS as a response variable, and the logarithm of time (in years) between randomization and the Min (EOS date, start of a new DMT for MS) as an offset variable. By checking the consistency of the treatment effect in this analysis with the effect observed in the main analysis, we evaluate whether a bias in evaluating the treatment effect has been introduced in the FAS analysis due to the decision to start a DMT.

9.6.5.5 ARR up to EOS for imputed confirmed relapses

Same analysis as for the main analysis, but with number of imputed confirmed relapses up to EOS as a response variable (relapses with missing confirmation status imputed as confirmed relapses). All other aspects of the model are as per the main analysis. This analysis is conducted to assess that no bias was introduced by missing confirmation status (e.g., due to EDSS not completed).

9.6.5.6 ARR post EOT + 7 days following premature treatment discontinuation

This analysis is similar to the analysis described for the primary efficacy variable, using a model with the number of confirmed relapses in the PTO as a response variable, treatment, stratification variables and the number of relapses in the year prior to study (≤ 1 [or missing] and ≥ 2) entry as factors and the logarithm of time between EOT + 8 days and EOS (in years) as an offset variable. The analysis is based on the Post-treatment observation period analysis set (FAS subjects prematurely discontinuing treatment with EOS date after EOT + 7 days).

9.6.5.7 ARR by time period

Confirmed relapses are analyzed by time period (up to Week 60, post Week 60, and in 12 week periods). The analysis is conducted separately for each period using descriptive statistics and fitting a model as for the primary efficacy variable (adjusting for the same covariates), with logarithm of observation time in the respective period (in years) as an offset variable. The following are displayed for each period: ARR with 95% CI per treatment arm, Rate ratio with 95% CI together with number of subjects included in the analysis.

9.6.5.8 Forest plot of primary efficacy analysis and main sensitivity / supplementary analyses

Results of the analyses will be summarized in forest plots containing: ARR including 99% CIs, by treatment (as text); Number of subjects by treatment (as text); Rate ratio including 99% CIs (as graphic); Dotted reference line at rate ratio = 1; Solid reference line for the primary analysis rate ratio; Indicators to the right and to the left of the reference line favoring ponesimod 20 mg or teriflunomide 14 mg; Treatment effect p-value (as text). The plot will be repeated presenting 95% CIs.

The following sensitivity analyses for the primary estimand will be displayed in one forest plot:

- Primary efficacy analysis for all confirmed relapses up to EOS, adjusted for the stratification variables (IRT) and the number of relapses in the year prior to study entry based on the FAS (as a reference);
- Sensitivity analysis for all confirmed relapses up to EOS, unadjusted based on the FAS;
- Sensitivity analysis for all confirmed relapses up to EOS, adjusted for derived stratification variables and the number of relapses in the year prior to study entry on the FAS;

Sensitivity analyses on the FAS for the primary estimand on handling missing data [see Section 9.6.4.3] will be displayed in a forest plot as well. It will contain the primary efficacy analysis, the MAR, Copy reference, and Jump to reference as well as a subset of results from the delta adjustment method.

The main supplementary analyses to the primary estimand will be displayed in a second forest plot:

- Primary efficacy analysis for all confirmed relapses up to EOS, adjusted for the stratification variables (IRT) and the number of relapses in the year prior to study entry based on the FAS (as a reference);
- Supportive analysis of all confirmed relapses up to EOT + 7 days, adjusted for the stratification variables (IRT) and the number of relapses in the year prior to study entry based on the FAS;
- Supportive analysis for all confirmed relapses up to EOS collected per-protocol, adjusted for the stratification variables (IRT) and the number of relapses in the year prior to study entry based on the PPS;
- Supportive analysis for all relapses up to EOS, adjusted for the stratification variables (IRT) and the number of relapses in the year prior to study entry based on the FAS.
- Supportive analysis for all relapses up to start of new disease modifying therapy (DMT) for MS, adjusted for the stratification variables (IRT) and the number of relapses in the year prior to study entry based on the FAS.
- Supportive analysis for ARR up to EOS for imputed confirmed relapses.

9.6.6 Other analyses related to the primary endpoint

9.6.6.1 Relapse characteristics and relapse symptoms

Relapse characteristics will be summarized using descriptive statistics on the FAS. This includes the following:

Number (%) of subjects with at least one: relapse, relapse requiring hospitalization, relapse treated with corticosteroids; for all relapses up to EOS, confirmed relapses up to EOS, all relapses up to EOT + 7 days, confirmed relapses up to EOT + 7 days.

Number (%) of relapses (out of total number of relapses) requiring hospitalization, treated with corticosteroids and descriptive statistics for continuous data for relapse duration (days); for all relapses up to EOS as well as for confirmed relapses up to EOS, all relapses up to EOT + 7 days, confirmed relapses up to EOT+7 days. Number (%) of relapses (out of total number of relapses) per relapse symptom category, as well as number of functional systems affected per relapse (out of total number of relapses) is summarized descriptively per category by treatment arm. It is conducted for all relapses up to EOS as well as for confirmed relapses up to EOS, all relapses up to EOT + 7 days, confirmed relapses up to EOT + 7 days.

9.6.6.2 Number of new or worsening neurological symptoms up to EOS

New or worsening neurological symptoms up to EOS are summarized overall and by sub-categories (confirmed relapse, non-confirmed relapse, symptoms not considered a relapse) using descriptive statistics by treatment arm. Percentages for sub-categories are presented out of the total number of new or worsening neurological symptoms.

New or worsening neurological symptoms are reported via a telephone interview or at the site in a face-to-face interview and at both these times a decision must be taken by the treating neurologist to refer the subject to the efficacy assessor. Once referred to the efficacy assessor the symptom is considered a relapse and is assessed for confirmation. To ensure there is no bias in the selection of symptoms considered as relapses between treatments, an analysis will compare the proportion of these new or worsening neurological symptoms that are considered as relapses or as confirmed relapses. If there is an imbalance in the selection between treatments, this will be explored further.

9.6.6.3 Change in the collection of the primary endpoint introduced by protocol amendment 3

To investigate the impact of protocol amendment 3, the cumulative time in the study with data collected under protocol version 3 or earlier (prior to switching to PV4) as a proportion of the total cumulative time in the study will be calculated. Depending on the proportion of data collected under each protocol, further supportive analysis will be introduced to assess the impact of the change in the method of the primary endpoint collection. The analysis is detailed in Section [9.3.1](#).

9.6.7 Subgroup analyses

Subgroup analyses for confirmed relapses up to EOS will be conducted on the subgroup variables listed in Section [8](#) using the FAS and will be repeated for a Per Protocol analysis. The analysis is conducted to assess consistency of the overall treatment effect across subgroup variables.

A separate NB model will be fitted within each subgroup level for confirmed relapses up to EOS, with treatment as the only covariate and the log of the time (in years) from randomization up to EOS as an offset variable. Estimates of ARR by treatment arm, rate ratio with 99% CIs within each subgroup level will be presented, accompanied by the number of subjects per category. The analysis is repeated presenting 95% CIs within each subgroup level.

The treatment-by-subgroup interaction p-value is estimated for each subgroup variable from a separate model including treatment, the subgroup and the treatment-by-subgroup interaction term(s) using a Likelihood ratio test. Interactions with a p-value < 0.01 will be investigated further to determine the nature of the interaction (quantitative or qualitative) and the association with other subgroups.

Results are presented in a summary table and in a forest plot. The forest plot will include the 'overall' treatment effect, based on the primary efficacy analysis as a reference line. Point estimates are presented within the forest plot with its size proportional to the number of subjects in the subgroup.

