9.6.3 Main analysis

The primary statistical analysis will be performed up to EOS on the FAS using an NB regression model for confirmed relapses, with treatment as a factor and the binary stratification variables (EDSS \leq 3.5 versus EDSS $>$ 3.5; DMT within last 2 years prior to randomization [Yes/No]) and the number of relapses in the year prior to study entry (categories \leq 1 [or missing, in order to avoid excluding subjects from the analysis] and \geq 2) included in the model. The model also includes an offset variable defined as the log of time on study (in years) from randomization up to EOS. The primary null hypothesis will be tested with a two-sided alpha level of 1% for conclusive evidence and 5% for a positive study.

Mean model-based estimates of the ARR (for confirmed relapses), by treatment arm, as well as 99% CIs and 95% CIs are presented. A rate ratio comparing ponesimod 20 mg with teriflunomide 14 mg will be derived from the model including 99% CIs, 95% CIs and the corresponding p-value. The dispersion parameter will also be displayed.

Descriptive summary statistics of the number of confirmed relapses as a continuous variable and the number of confirmed relapses in categories (0, 1, 2, 3, 4, ≥ 5), by treatment arm will be presented. The total cumulative number of confirmed relapses, as well as the total cumulative time on study (summed for all subjects) will also be displayed. From the total number of confirmed relapses and the total time on study the raw unadjusted ARR, by treatment arm, will be calculated and summarized.

The fit of the model will be assessed and other distributions such as the Poisson distribution will be considered in case of a lack of fit. The treatment-by-covariate interactions will also be assessed in separate models; if the interaction p-value is < 0.01 it will be investigated further to determine the nature of the interaction (quantitative or qualitative).

Handling of study discontinuation

For the main analysis it is assumed that follow-up time after study discontinuation is missing at random: a hypothetical scenario is considered assuming that subjects who discontinued the study would have similar efficacy as the subjects from the same treatment group who did not discontinue the study.

Sensitivity analyses on this assumption are described in Section [9.6.4](#).

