9.7.1.5 Subgroup analyses

Subgroup analyses for change from baseline to Week 108 in FSIQ-RMS symptoms score will be conducted on the subgroup variables listed in Section 8, apart from recruitment period, using the FAS. The analysis is conducted to assess consistency of the overall treatment effect across subgroup variables.

The above main MMRM analysis will be repeated within subgroup levels using a model as for the main analysis without adjustments for stratification factors. Estimates of mean at Week 108 by treatment arm, difference in means with 95% CIs within each subgroup level will be presented, accompanied by the number of subjects per category.

The treatment-by-subgroup interaction p-value is estimated for each subgroup variable from a separate model including treatment, the subgroup and the treatment-by-subgroup interaction term(s). Interactions with a p-value < 0.01 will be investigated further to determine the nature of the interaction (quantitative or qualitative) and the association with other subgroups.

Results are presented in a summary table and in a forest plot. The forest plot will include the 'overall' treatment effect, based on the main efficacy analysis as a reference line. Point estimates are presented within the forest plot with its size proportional to the number of subjects in the subgroup.

9.7.2 Analysis of cumulative unique active lesions from baseline up to Week 108 (CUAL)

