9.7.2.2 Statistical analysis

The main analysis of the secondary endpoint CUAL will be performed on the FAS using a negative binomial regression model with treatment as a factor and the binary stratification variables (EDSS \leq 3.5 versus EDSS > 3.5; DMT within last 2 years prior to randomization [Yes/No]) and Gd+ T1 lesions at baseline (absent or present) included in

the model. The model also includes an offset variable defined as the log of the time up to last MRI (in years) considered for analysis.

Mean model-based estimates of the number of CUALs per year will be provided by treatment group, as well as 95% Wald CIs. A rate ratio comparing ponesimod 20 mg with teriflunomide 14 mg will be derived from the model including 95% Wald CIs and the corresponding p-value. The dispersion parameter will also be displayed.

The fit of the model will be assessed and other distributions such as the Poisson distribution will be considered in case of a lack of fit.

Descriptive summary statistics of the number of CUALs up to Week 108 continuous and in categories (0, 1–5, 6–10, 11+) will be presented. The total number of CUALs as well as the total cumulative time up to the last MRI scan (summed for all subjects) will also be displayed. From the total number of CUALs and the total cumulative time up to the last MRI scan the raw number of CUALs per year will be calculated and summarized.

A listing of CUAL data will be presented.

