The main analysis will be repeated using the number of CUALs up to EOT + 7 days as a response variable, and the log of the time to the last MRI scan (years) considered in this analysis as an offset variable [see Section 10.1], using the FAS. Covariate adjustment as for the main analysis will be applied.

9.7.2.4 *Subgroup analyses*

Subgroup analyses for CUAL from baseline to Week 108 will be conducted on the subgroup variables listed in Section 8, apart from recruitment period, using the FAS. The analysis is conducted to assess consistency of the overall treatment effect across subgroup variables.

From a methodological point of view subgroup analyses as for the primary endpoint will be applied, with results presented in a table and a forest plot.

9.7.3 **Analysis of Time to 12-week CDA**

9.7.3.1 *Hypothesis and statistical model*

Hypotheses are formulated in terms of survival functions $S(t)$, i.e., the probability that time to 12-week CDA is $\geq t$ for a day t relative to the date of randomization. Two-sided hypotheses are expressed in terms of the survival functions $S_{P20mg}(t)$ and $S_{T14mg}(t)$.

$$H_{0,CDA}: S_{P20mg}(t) = S_{T14mg}(t) \text{ for all } t \geq 0$$

vs.

$$H_{1,CDA}: S_{P20mg}(t) \neq S_{T14mg}(t) \text{ for all } t \geq 0$$

The null hypothesis will be tested using a two-sided stratified log-rank test. The p-value will be compared to the local significance level as per the overall testing strategy [see Section 9.1].

9.7.3.2 *Statistical analysis*

The main analysis on ‘Time to 12-Week CDA up to EOS’ will be performed on the FAS by a two-sided stratified log-rank test with stratification factors (EDSS \leq 3.5 versus EDSS $>$ 3.5; DMT within last 2 years prior to randomization [Yes/No]) as stratification variables.

In addition, hazard ratio and 95% CI based on a stratified Cox regression will be provided. The model will include treatment as factor, and the same covariates as for the log-rank analysis as stratification variables.

Data are summarized in a table including, number of subjects with event / censored, Kaplan-Meier estimates (unstratified) and corresponding CI (anticipated time points: 12, 24, ..., 108 weeks), and median (as well as 25th and 75th percentiles) of the survival function together with CIs. A graphical display presenting a Kaplan-Meier plot (unstratified) going upward is presented including CIs at specific time points as well as the log-rank p-value, hazard ratio and CI from the main analysis.

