9.7.3.4 Subgroup analyses

Subgroup analyses for time to 12-week CDA up to EOS on the FAS will be conducted on the subgroup variables listed in Section 8 (apart from ‘recruitment period’) using the FAS. The analysis is conducted to assess consistency of the overall treatment effect across subgroup variables.

Separate Cox regression models will be fitted within each subgroup level using only treatment as a factor and no other covariates. The hazard ratio and 95% CI of the treatment effect within each subgroup level will be displayed, accompanied by number of subjects with events / censored.

The treatment-by-subgroup interaction p-value is estimated for each subgroup variable from a separate model including treatment, the subgroup and the treatment-by-subgroup interaction term(s).

Results are presented in a summary table and in a forest plot. The forest plot will include the ‘overall’ treatment effect, based on the primary efficacy analysis as a reference line. Point estimates are presented within the forest plot with its size proportional to the number of events in the subgroup.

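### Subgroup models for ARR, CUAL and CDA omit the main-analysis covariates or strata; the material loss is the baseline Gd+ adjustment in CUAL, a precision cost in exploratory analyses that is cheap to avoid

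*SAP*

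**What the plan says.** - **ARR.** The main model (9.6.3) contains treatment, the EDSS and DMT strata, and "the number of relapses in the year prior to study entry (categories" of at most one or at least two), with log time as offset. The subgroup model (9.6.7) is fitted within each level "with treatment as the only covariate and the log of the time (in years) from randomization up to EOS as an offset variable". The interaction p-value comes "from a separate model including treatment, the subgroup and the treatment-by-subgroup interaction term(s) using a Likelihood ratio test".
- **CUAL.** The main model (9.7.2.2) contains the two strata and "Gd+ T1 lesions at baseline (absent or present) included in" the model. For subgroups, 9.7.2.4 says: "From a methodological point of view subgroup analyses as for the primary endpoint will be applied".
- **12-week CDA.** The main analysis (9.7.3.2) is a log-rank test and Cox model stratified by EDSS and DMT. The subgroup Cox models (9.7.3.4) are fitted "using only treatment as a factor and no other covariates". The 24-week subgroup section, which is the second section numbered 9.7.1.5, uses the same methods.
- **FSIQ-RMS.** The subgroup section (the first 9.7.1.5) repeats the MMRM "using a model as for the main analysis without adjustments for stratification factors". Its interaction model is described only as treatment, subgroup and their interaction.
- **Display.** For ARR: "The forest plot will include the 'overall' treatment effect, based on the primary efficacy analysis as a reference line". CUAL inherits this, and the FSIQ-RMS and 12-week CDA sections say much the same.

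**The concern.** The stated purpose is to judge whether the treatment effect is consistent across subgroups. Scatter around the reference line should then reflect heterogeneity as far as possible, not a change of model. Most subgroup variables in Section 8 (sex, age, region, MS subtype, highly active disease) were not randomization strata. A prognostic factor such as baseline Gd+ is therefore balanced within their levels only by chance, and the subgroup model no longer corrects for it.

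Two things are at stake: wider intervals with a weaker interaction test, and a visual comparison of subgroup estimates from one kind of model with an overall estimate from another. The other planned CUAL analyses (imputation, per-protocol, up to EOT + 7 days; 9.7.2.3) all keep the main covariates. The subgroup analyses are the exception, and no reason is given.

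**Working it through.** The SAP states no precision or power for subgroups, so there is no figure to reproduce.

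**Step 1: what each subgroup model loses**

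| Endpoint | Dropped within levels | Kept |
|---|---|---|
| ARR | EDSS, DMT, prior relapses | treatment, offset |
| CUAL | EDSS, DMT, baseline Gd+ | treatment, offset |
| CDA, 12- and 24-week | stratification by EDSS and DMT | treatment |
| FSIQ-RMS | EDSS, DMT | baseline score, baseline by visit, and the rest of the MMRM |

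**Step 2: formulas for a negative binomial log rate ratio**

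Let n be subjects per arm in a subgroup level, μ the mean count, k the dispersion, p the covariate prevalence and r its rate ratio.

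- CV² = p(1−p)(r−1)² / (1−p+pr)²
- Unadjusted variance = (2/n)(1/μ + k_u), where k_u = (1+k)(1+CV²) − 1
- Adjusted variance = 2 / [n Σ w_x μ_x/(1+kμ_x)], summed over the covariate levels x with weights w_x
- Shift in the unadjusted log rate ratio from a one-SD chance imbalance = √(2p(1−p)/n) × (r−1)/(1−p+pr)

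All inputs are assumptions: p = 0.4; for CUAL 1.5 to 3 lesions per year over 2 years and k of 0.8 to 1.5; for ARR a rate of 0.2 to 0.3 over 756/365.25 = 2.07 years and k of 0.5 to 1.

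**Step 3: one CUAL case in full** (n = 100 per arm, μ = 1.5 × 2 = 3, k = 0.8, r = 3)

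- 1−p+pr = 1.8, so CV² = 0.24 × 4/3.24 = 0.296 and k_u = 1.8 × 1.296 − 1 = 1.333.
- Unadjusted variance = 0.02 × (0.333 + 1.333) = 0.0333 (SE 0.183).
- Stratum means are 3/1.8 = 1.667 and 5. The sum is 0.6 × 1.667/2.333 + 0.4 × 5/5 = 0.829.
- Adjusted variance = 0.02/0.829 = 0.0241 (SE 0.155).
- Ratio = 0.0333/0.0241 = 1.38.
- Imbalance shift = √0.0048 × 2/1.8 = 0.077, about half the adjusted SE. At r = 2 it is 0.069/1.4 = 0.049.

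**Step 4: over the assumed ranges**

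| Endpoint, covariate | r | Extra variance when dropped |
|---|---|---|
| CUAL, Gd+ | 1.5 | 5–7% |
| CUAL, Gd+ | 2 | 15–21% |
| CUAL, Gd+ | 3 | 34–49% |
| ARR, prior relapses | 1.3 | 0.6–0.9% |
| ARR, prior relapses | 1.5 | 1.5–2.2% |
| ARR, prior relapses | 2 | 4.5–6.4% |

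**Step 5: simulation check for CUAL** (300 runs per setting, k = 1, true rate ratio 0.6)

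Variance ratios were 1.16 (r = 2, 100 per arm), 1.27 (r = 3, 100 per arm) and 1.39 (r = 3, 250 per arm). Formula and simulation together give roughly 27–49% at r = 3. Mean unadjusted log rate ratios were −0.50 to −0.52 against a true −0.51, so no systematic bias appears.

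**Step 6: what this means for CUAL**

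Intervals are wider by the square root of the variance ratio: 7–10% at r = 2 (√1.15 to √1.21) and 13–22% at r = 3 (√1.27 to √1.49). At r = 3 the loss equals discarding 1 − 1/1.27 = 21% to 1 − 1/1.49 = 33% of the level.

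**The case against.** The case against is substantial, and much of it stands.

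- A reader might infer that every subgroup analysis drops its covariates. The FSIQ-RMS within-level models do not: baseline score and baseline-by-visit remain. Whether its interaction model keeps them is unstated.
- A reader might infer that the count-endpoint subgroup estimates are biased or aim at something other than the reference line. With a log link and randomization, the covariate-adjusted and unadjusted rate ratios share a target when the treatment effect is common across covariate levels. The unadjusted intervals also already carry the extra variance.
- For the primary endpoint the harm is close to nil, and a sparse model has a convergence advantage in small levels.
- Like-for-like overall estimates are already planned for ARR (9.6.4.1, plotted under 9.6.5.8) and for both CDA endpoints (9.7.3.3 and the 24-week 9.7.1.4). Section 9.6.3 also tests treatment by the ARR model's own covariates.
- Where the subgroup variable is itself a main-model covariate, little or nothing is lost for that covariate within levels.
- Tests outside the hierarchy are exploratory under 9.1.1, and an ARR interaction below 0.01 only triggers further investigation.
- The size of the CUAL loss depends on how prognostic Gd+ is, and the document does not say.

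What these points leave in place is the loss of Gd+ in CUAL, where no unadjusted overall analysis is planned, and the stratified-versus-unstratified comparison for CDA.

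**Conclusion.** The point holds, centred on CUAL. Dropping baseline Gd+ enlarges the variance of subgroup log rate ratios by about 5–7%, 15–21% and 27–49% at assumed Gd+ rate ratios of 1.5, 2 and 3, and exposes them to chance Gd+ imbalance. If both levels have similar Gd+ prevalence, the interaction contrast loses precision by the same proportion.

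For ARR the loss is about 1–6% in variance over assumed rate ratios of 1.3 to 2, so change there is mainly for alignment. For CDA, unstratified and stratified hazard ratios can differ in target, so part of any gap from the reference line could come from the model; no size was computed.

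The documents do not support calling this an error in a confirmatory result. It is an avoidable inefficiency in prespecified exploratory analyses, worth correcting because the correction is nearly free.

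**What to change.** - **CUAL (9.7.2.4).** Keep baseline Gd+ and the two strata in the subgroup and interaction models. Preferably fit one FAS model per subgroup variable with treatment, subgroup, their interaction and the main covariates, and take both the subgroup contrasts and the interaction p-value from it.
- **Overlap.** Omit any covariate that is the subgroup variable or a near-duplicate of it. Section 8 lists both IRT and eCRF versions of EDSS and DMT, so the IRT version should go when the subgroup is the eCRF one. State how highly active disease is handled, since 5.2.2 builds it partly from DMT use, relapses, EDSS and Gd+.
- **CDA.** Use the stratified Cox model, or draw the already planned unstratified overall hazard ratio as the reference line.
- **ARR.** Do the equivalent for alignment: keep the main covariates, or draw the planned unadjusted overall rate ratio.
- **FSIQ-RMS.** State whether the interaction model keeps the baseline and visit terms.
- **Check.** Retain the treatment-only within-level models as a secondary display.

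The cost is SAP wording and a few lines of code, with no new data. The downside is that a pooled model assumes common dispersion and covariate effects across levels; the retained within-level models show whether that matters. Pooling also eases fitting in small levels.
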